A study evaluated the PK of eribulin in patients with mild (Child-Pugh A; $n=7$) and moderate (Child-Pugh B; $n=4$) hepatic impairment due to liver metastases. Compared to patients with normal hepatic function ($n=6$), eribulin exposure increased 1.8-fold and 3-fold in patients with mild and moderate hepatic impairment, respectively. Administration of eribulin at a dose of 0.97 mg/m^2 to patients with mild hepatic impairment and 0.62 mg/m^2 to patients with moderate hepatic impairment resulted in a somewhat higher exposure than after a dose of 1.23 mg/m^2 to patients with normal hepatic function. Eribulin was not studied in patients with severe hepatic impairment (Child-Pugh C). There is no study in patients with hepatic impairment due to cirrhosis.

Renal impairment

A study in patients with different degrees of impaired renal function showed that the exposure of eribulin in patients with moderate renal function (creatinine clearance ≥ 40 to 59 ml/min , $n=6$) was similar to patients with normal renal function while the exposure in patients with severe impairment was increased by 75% (creatinine clearance $< 40 \text{ ml/min}$, $n=4$).

Elderly population

In studies of 1,222 patients treated with eribulin, 244 patients (20.0%) were $> 65 - 75$ years of age and 66 patients (5.4%) were > 75 years of age. Among the 827 of these patients who received the recommended dose of eribulin in the Phase 2/3 breast cancer studies, 121 patients (14.6%) were $> 65 - 75$ years of age and 17 patients (2.1%) were > 75 years of age. The safety profile of eribulin in elderly patients (> 65 years of age) was similar to that of patients ≤ 65 years of age. No dose adjustments are recommended for the elderly population.

Pregnancy

There are no data from the use of eribulin in pregnant women. Eribulin is embryotoxic, foetotoxic and teratogenic in rats. Eribulin should not be used during pregnancy and women of childbearing potential must be advised to avoid becoming pregnant whilst they are receiving eribulin by using effective contraception during and up to 3 months after treatment.

For the most up to date safety information, please refer to the most current edition of the Investigator's Brochure.

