8.2.2.1 Permitted study drug dose adjustments and interruptions

For patients who are unable to tolerate the protocol-specified dosing scheme, dose adjustments and interruptions are permitted in order to keep the patient on the study drugs. The following guidelines should be followed.

These changes must be recorded on the Dosage Administration Record eCRF.

For patients with start dose of 5 mg daily and well tolerated treatment, increasing of everolimus dose to 10 mg daily is recommended according to the approved label.

Treatment with everolimus and standard endocrine therapy should continue as long as clinical benefit is observed or until unacceptable toxicity occurs. Management of severe and/or intolerable suspected adverse events may require temporary dose reduction and/or interruption.

For patients who do not tolerate the protocol-specified everolimus dosing schedule, dose adjustments are permitted in order to allow the patient to continue the study. The following guidelines need to be applied:

Dose adjustments are permitted for any adverse event suspected to be related to everolimus in those patients unable to tolerate their individual once daily oral dose. If administration of everolimus must be interrupted because of unacceptable toxicity, everolimus dosing will be interrupted or modified according to the guidelines in TABLE 14, TABLE 15 and TABLE 16 below.

In addition, if any surgery is planned, everolimus dosing should be interrupted one week prior to surgery and should be re-started as soon as possible after wound healing.

If everolimus dosing is interrupted due to toxicity, everolimus should not be resumed unless recovery to grade ≤ 1 is achieved in less than 4 weeks. Then everolimus could be reintroduced at the initial dose or a lower dose level depending on the toxicity type and grade(see TABLE14 , TABLE 15 and TABLE 16 below).

All study drug interruptions or dose modifications must be recorded on the Dosage Administration Record page of the eCRF.

Dose level	Dose and schedule
0 = starting dose	Last administered daily dose
-1 dose level	5 mg daily (if starting dose 10 mg daily)
	5 mg every other day (if starting dose 5 mg daily).

Minimal dose is 5 mg every other day.

Table 14: Everolimus dose reduction

If a patient has already decreased everolimus intake to 5 mg every other day, no further dose reduction is permitted. Patients requiring an additional everolimus dose reduction will be required to discontinue study treatment.

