8.4.2.1 Permitted study drug dose adjustments and interruptions

Treatment with eribulin should continue as long as clinical benefit is observed or until unacceptable toxicity occurs. Management of severe and/or intolerable suspected adverse events may require temporary dose reduction and/or interruption.

For patients who do not tolerate the protocol-specified eribulin dosing schedule, dose adjustments are permitted in order to allow the patient to continue the study. The following guidelines need to be applied: Dose adjustments are permitted for any adverse event suspected to be related to eribulin in those patients unable to tolerate the normal dose. If administration of eribulin must be interrupted because of unacceptable toxicity, eribulin dosing will be interrupted or modified according to the guidelines in TABLE 15 below.

All study drug interruptions or dose modifications must be recorded on the Dosage Administration Record page of the eCRF.

For patients who are unable to tolerate the protocol-specified dosing scheme, dose adjustments and interruptions are permitted in order to keep the patient on the study drugs. The following guidelines should be followed.

The administration of eribulin should be delayed on Day 1 or Day 8 for any of the following:

- Absolute neutrophil count (ANC) < 1000/μl
- Platelets < 75000/μl
- Grade 3 or 4 non-hematological toxicities.

Patients who interrupt eribulin therapy for more than 4 weeks must be discontinued from the study.

Dose reduction during therapy

Dose reduction recommendations for retreatment are shown in the following TABLE 24.

Adverse reaction after previous eribulin administration	Recommended dose of eribulin
Haematological:	
ANC < 0.5 x 10 ⁹ /l lasting more than 7 days	0.97 mg/m²
ANC < 1 x 10 ⁹ /l neutropenia complicated by fever or infection	
Platelets < 25 x 10 ⁹ /l thrombocytopenia	
Platelets < 50 x 10 ⁹ /l thrombocytopenia complicated by haemorrhage or requiring blood or platelet transfusion	
Non-haematological:	
Any Grade 3 or 4 in the previous cycle	
Reoccurrence of any haematological or non-haematological adverse reactions as specified above:	
Despite reduction to 0.97 mg/ m ²	0,62 mg/m²
Despite reduction to 0.62 mg/m ²	Consider discontinuation

Table 24: Eribulin dose modification guidelines for toxicities.

Do not re-escalate the eribulin dose after it has been reduced.

Patients with hepatic impairment

Impaired liver function due to metastases:

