The recommended dose of eribulin in patients with mild hepatic impairment (Child-Pugh A) is 0.97 mg/m² administered intravenously over 2 to 5 minutes on Days 1 and 8 of a 21-day cycle. The recommended dose of eribulin in patients with moderate hepatic impairment (Child-Pugh B) is 0.62 mg/m² administered intravenously over 2 to 5 minutes on Days 1 and 8 of a 21-day cycle.

Severe hepatic impairment (Child-Pugh C) has not been studied but it is expected that a more marked dose reduction is needed if eribulin is used in these patients.

Impaired liver function due to cirrhosis:

This patient group has not been studied. The doses above may be used in mild and moderate impairment but close monitoring is advised as the doses may need readjustment.

Patients with renal impairment

Patients with severely impaired renal function (creatinine clearance <40 ml/min) may need a reduction of the dose (see section 3.3.7). The optimal dose for this patient groups remains to be established.

Caution and close safety monitoring as advised. No specific dose adjustments are recommended for patients with mild to moderate renal impairment.

Elderly patients

No specific dose adjustments are recommended based on the age of the patient.

These changes must be recorded on the Dosage Administration Record eCRF.

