8.4.3.1 Management of specific toxicities

Neutropenia

The neutropenia observed was reversible and not cumulative; the mean time to nadir was 13 days and the mean time to recovery from severe neutropenia (< 500/ μ l) was 8 days. Neutrophil counts of < 500/ μ l that lasted for more than 7 days occurred in 13% of breast cancer patients treated with eribulin. Neutropenia resulted in discontinuation in < 1% of patients receiving eribulin.

Severe neutropenia may be managed by the use of G-CSF or equivalent at the physician's discretion in accordance with relevant guidelines. 18% of breast cancer patients treated in a phase 3 study with eribulin received G-CSF.

Peripheral neuropathy

In the 827 breast cancer patients the most common adverse reaction resulting in discontinuation of treatment with eribulin was peripheral neuropathy (4%). The median time to Grade 2 peripheral neuropathy was 85 days (post 4 cycles). Development of Grade 3 or 4 peripheral neuropathy occurred in 7% of eribulin treated breast cancer patients. In clinical trials, patients with pre-existing neuropathy were as likely to develop new or worsening symptoms as those who entered the study without the condition. In patients with pre-existing Grade 1 or 2 peripheral neuropathy the frequency of treatment-emergent Grade 3 peripheral neuropathy was 10%.

In case of Neuropathy > grade 2 treatment with eribulin should be withheld until recovery to grade 0-2. Continue therapy with a reduced dose of 1 dose level.

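### Table 24 states eribulin reductions as fixed doses that work only from a 1.23 mg/m² start: a Child-Pugh A patient dosed at 0.97 gets no reduction after a first severe toxicity, which for neuropathy conflicts with section 8.4.3.1

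*Protocol*

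**What the plan says.** Section 8.4.1.9 starts eribulin at 1.23 mg/m² on days 1 and 8 of a 21-day cycle. For toxicity during treatment, section 8.4.2.1 states "Dose reduction recommendations for retreatment are shown in the following TABLE 24". The table has two parts:

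- First listed toxicity: four haematological triggers and one non-haematological trigger ("Any Grade 3 or 4 in the previous cycle") share a single dose, 0.97 mg/m².
- Later events: under "Reoccurrence of any haematological or non-haematological adverse reactions as specified above", a patient already reduced to 0.97 goes to 0.62 mg/m², and one already reduced to 0.62 is considered for discontinuation.

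A sentence below the table forbids going back up after a reduction. The hepatic-impairment text then follows in the same section: "The recommended dose of eribulin in patients with mild hepatic impairment (Child-Pugh A) is 0.97" mg/m², and "The recommended dose of eribulin in patients with moderate hepatic impairment (Child-Pugh B) is 0.62" mg/m². It does not say how Table 24 applies to patients on those doses.

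Section 8.4.3.1 tells the investigator to withhold eribulin for neuropathy above grade 2 until it recovers to grade 0-2, and then: "Continue therapy with a reduced dose of 1 dose level". Section 8.4 defines no eribulin dose levels.

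The ineligibility criteria in section 5 name Child-Pugh classes B and C as examples of excluded liver dysfunction. They except, among others, liver metastases and stable chronic non-viral liver disease. Class A is not named.

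**The concern.** A reduction table written in absolute doses assumes that every patient starts at the same dose. Here the section that contains the table sets three possible starting doses. A patient started at 0.97 who has a first listed toxicity is directed to 0.97. She therefore resumes at the dose that caused a severe event.

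These patients also have little margin. Section 3.4.6 reports that "eribulin exposure increased 1.8-fold and 3-fold in patients with mild and moderate hepatic impairment, respectively", and adds that 0.97 in mild impairment still gave somewhat higher exposure than 1.23 with normal liver function.

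For severe neuropathy an investigator also meets two explicit rules that give different doses for the same event. What is at stake is dosing safety and uniform conduct across up to 100 centers.

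**Working it through.** **Inputs**

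- Starting doses: 1.23 mg/m² (8.4.1.9); 0.97 for Child-Pugh A and 0.62 for Child-Pugh B (8.4.2.1, hepatic impairment).
- First-toxicity dose: 0.97 (8.4.2.1, Table 24).
- Neuropathy above grade 2: one level down (8.4.3.1). No levels are defined, so the only sequence available is the table's own: 1.23, 0.97, 0.62.

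**Step 1. Size of the first reduction, as 1 − new dose / current dose**

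- Start 1.23, Table 24 gives 0.97: 1 − 0.97/1.23 = 0.211, a reduction of 21%.
- Start 0.97, Table 24 gives 0.97: 1 − 0.97/0.97 = 0, no reduction.
- Start 0.97 if the next level were used, 0.62: 1 − 0.62/0.97 = 0.361, a reduction of 36%.
- Start 0.62: the table's first-toxicity dose is not below the current dose, so there is no valid reduction step.

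**Step 2. Can the 0.62 row be used at a first event?** That row has two conditions: the reaction has recurred, and it did so despite a reduction to 0.97. A hepatic starting dose might be counted as already reduced, which would meet the second condition. A first event is still not a recurrence, so the first condition fails.

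**Step 3. Neuropathy above grade 2, both rules side by side.** Neuropathy above grade 2 falls under the table's non-haematological trigger for grade 3 or 4 events.

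| Current dose (mg/m²) | Table 24, first event | Section 8.4.3.1, one level down | Agree? |
|---|---|---|---|
| 1.23 | 0.97 | 0.97 (inferred) | yes |
| 0.97 | 0.97 | 0.62 (inferred) | no |
| 0.62 | no valid step | no lower level exists | undefined |

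**Step 4. How often the triggers occur.** Section 8.4.3.1 reports grade 3 or 4 neuropathy in 7% of eribulin-treated breast cancer patients, and neutrophils below 500/µl for more than 7 days in 13%. Both figures are for all treated patients. The protocol does not say how many will start at 0.97 or 0.62, so no patient count can be derived.

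**Step 5. Comparison within the protocol.** For everolimus, Table 14 makes the first step depend on the starting dose: 5 mg daily after a 10 mg start, and "5 mg every other day (if starting dose 5 mg daily"). For ribociclib, Table 19 lists successive reductions. Neither provision exists for eribulin.

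**The case against.** Four arguments deserve weight.

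*The table guides and does not bind.* It is introduced as recommendations, section 8.4.2 allows doses to be held or reduced for adverse events, and nothing forbids 0.62 for a patient already at 0.97. That is fair, and many investigators would do this. But section 8.4.2.1 also says its guidelines have to be applied, and the stated dose for the event is 0.97.

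*Section 8.4.2 defers to the product information and investigator's brochure, and asks sites to consult the study office before continuing after a delay of more than two weeks.* Those documents are not available here and may cover hepatic starting doses. A general reference does not settle a conflict between two rules inside the protocol, and the consultation rule covers only longer delays.

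*Section 8.4.3.1 is the more specific rule and should govern neuropathy.* This is a reasonable way to resolve the mismatch, but the protocol does not state it. It also leaves the other listed toxicities with no reduction for a 0.97 start.

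*Another drug's table proves nothing about Table 24.* Agreed. It shows only that clearer drafting was within reach.

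A reader might also infer that a patient started at 0.62 would have her dose raised to 0.97. The documents do not support that. The table sits under a dose-reduction heading, the sentence below it bars re-escalation, and the hepatic text speaks of a more marked reduction for Child-Pugh C, which treats the lower hepatic doses as reductions. Child-Pugh B is also named among the exclusions, so such a patient enters only through an arguable exception.

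**Conclusion.** The point holds for patients who start at 0.97 mg/m². As written, Table 24 gives them a 0% reduction after a first listed severe toxicity, where a patient starting at 1.23 gets 21%. For neuropathy above grade 2 it contradicts section 8.4.3.1. For a patient started at 0.62 the table is silent in effect: it has no usable first step, and nothing in it should be read as an instruction to increase the dose.

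The conclusion rests on the table's recurrence condition being read as worded, and on Child-Pugh A patients being eligible because the exclusion does not name them. The 0.62 figure for one level below 0.97 is inferred from the table's sequence, since no levels are defined.

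The likely number of patients affected is small and cannot be computed from the protocol. Estimating exposure at each dose would add little: the hepatic study compared groups of 7, 4 and 6 patients, and the text does not say whether its ratios are per unit dose. Endpoints, sample size and analysis are not affected. This is a dosing rule that should be corrected, and it does not threaten the trial's conclusions.

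**What to change.** In section 8.4.2.1, define the eribulin dose levels as 1.23, 0.97 and 0.62 mg/m². Restate Table 24 so that each listed toxicity leads one level below the current dose:

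- 1.23 to 0.97 (21% lower, unchanged from now);
- 0.97 to 0.62 (36% lower);
- 0.62 to consider discontinuation.

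State that this applies whatever the starting dose, and that no patient is dosed above her starting dose. The one-level step in section 8.4.3.1 then agrees with the table for 1.23 and 0.97. Add there that from 0.62 the step is to consider discontinuation.

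In the same amendment, change the reference in section 8.4.2.1 from Table 15, which covers non-haematological toxicities of everolimus, to Table 24. The reference in section 8.4.2 to section 8.3.2.1, which concerns ribociclib, should point to 8.4.2.1.

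The cost is one restated table and a few corrected references. No patients, visits or procedures are added, and the first step for patients starting at 1.23 does not change.

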8.4.3 Known undesirable effects of the study drugs

Unless otherwise noted, the TABLE shows the incidence rates of adverse reactions observed in 827 breast cancer patients who received the recommended dose in two Phase 2 and one Phase 3 study. Frequency categories are defined as: very common ($\geq 1/10$), common ($\geq 1/100$ to $< 1/10$), uncommon ($\geq 1/1,000$ to $< 1/100$), rare ($\geq 1/10,000$ to $< 1/1,000$) and very rare ($< 1/10,000$).

Within each frequency grouping, undesirable effects are presented in order of decreasing frequency. Where Grade 3 or 4 reactions occurred with a frequency of $\geq 1\%$, the actual total frequency and the frequency of Grade 3 or 4 reactions are given.

System Organ Class	Adverse Reactions – all Grades			
	Very Common (Frequency %)	Common (Frequency %)	Uncommon	Rare
Infections and infestations		Urinary tract infection Oral candidiasis Upper respiratory tract infection Nasopharyngitis Rhinitis	Pneumonia Neutropenic sepsis Oral herpes Herpes zoster	
Blood and lymphatic disorders	Neutropenia (54.5%) (G3/4: 48.3%) Leukopenia (22.1%) (G3/4: 14%) Anaemia (20.3%) (G3/4: 1.4%)	Febrile neutropenia (4.7%) (G3/4: 4.6%) ^a Thrombocytopenia Lymphopenia		Disseminated intravascular coagulation ^d
Metabolism and nutrition disorders	Decreased appetite	Hypokalaemia Hypomagnesaemia Dehydration Hyperglycaemia Hypophosphataemia		
Psychiatric disorders		Insomnia Depression		
Nervous system disorders	Peripheral neuropathy ^b (32.0%) (G3/4: 6.9%) Headache	Dysgeusia Dizziness Hypoesthesia Lethargy Neurotoxicity		

System Organ Class	Adverse Reactions – all Grades			
	Very Common (Frequency %)	Common (Frequency %)	Uncommon	Rare
Eye disorders		Lacrimation increased Conjunctivitis		
Ear and labyrinth disorders		Vertigo	Tinnitus	
Cardiac disorders		Tachycardia		
Vascular disorders		Hot flush	Deep vein thrombosis Pulmonary embolism	
Respiratory, thoracic and mediastinal disorders		Dyspnoea Cough Oropharyngeal pain Epistaxis Rhinorrhoea	Interstitial lung disease	
Gastrointestinal disorders	Nausea (35.1%) (G3/4: 1.1%) Constipation Diarrhoea Vomiting	Abdominal pain Stomatitis Dry mouth Dyspepsia Gastroesophageal reflux disease Mouth ulceration Abdominal distension		Pancreatitis ^d

Hepatobiliary disorders		Alanine aminotransferase increased (3.0%) (G3/4: 1.1%) ^c Aspartate aminotransferase increased	Hyperbilirubinaemia	
Skin and subcutaneous tissue disorders	Alopecia	Rash Pruritus Nail disorder Night sweats Palmar plantar erythrodysesthesia Dry skin Erythema Hyperhidrosis	Angioedema	
Musculoskeletal and connective tissue disorders	Arthralgia and Myalgia	Pain in extremity Muscle spasms Musculoskeletal pain and musculoskeletal chest pain Muscular weakness Bone pain Back pain		
Renal and urinary disorders			Dysuria Haematuria Proteinuria Renal failure	
General disorders and administration site conditions	Fatigue/Asthenia (52.8%) (G3/4 : 8.4%) Pyrexia	Mucosal Inflammation (9.8%) (G3/4: 1.3%) ^c Peripheral oedema Pain Chills Influenza like illness Chest Pain		
System Organ Class	Adverse Reactions – all Grades			
	Very Common (Frequency %)	Common (Frequency %)	Uncommon	Rare
Investigations		Weight decreased		

Table 25: Known undesirable effects of eribulin

Eribulin may cause adverse reactions such as tiredness and dizziness which may lead to a minor or moderate influence on the ability to drive or use machines. Patients should be advised not to drive or use machines if they feel tired or dizzy.

8.4.3.1 Management of specific toxicities

Neutropenia

The neutropenia observed was reversible and not cumulative; the mean time to nadir was 13 days and the mean time to recovery from severe neutropenia (< 500/ μ l) was 8 days. Neutrophil counts of < 500/ μ l that lasted for more than 7 days occurred in 13% of breast cancer patients treated with eribulin. Neutropenia resulted in discontinuation in < 1% of patients receiving eribulin.

Severe neutropenia may be managed by the use of G-CSF or equivalent at the physician's discretion in accordance with relevant guidelines. 18% of breast cancer patients treated in a phase 3 study with eribulin received G-CSF.

Peripheral neuropathy

In the 827 breast cancer patients the most common adverse reaction resulting in discontinuation of treatment with eribulin was peripheral neuropathy (4%). The median time to Grade 2 peripheral neuropathy was 85 days (post 4 cycles). Development of Grade 3 or 4 peripheral neuropathy occurred in 7% of eribulin treated breast cancer patients. In clinical trials, patients with pre-existing neuropathy were as likely to develop new or worsening symptoms as those who entered the study without the condition. In patients with pre-existing Grade 1 or 2 peripheral neuropathy the frequency of treatment-emergent Grade 3 peripheral neuropathy was 10%.

In case of Neuropathy > grade 2 treatment with eribulin should be withheld until recovery to grade 0-2. Continue therapy with a reduced dose of 1 dose level.

8.5 Concomitant Therapy

The investigator should instruct the patient to notify the study site about any new medications she takes after the start of the study drug. The electronic case report forms (eCRFs) will capture the use of all drugs, over-the-counter medications, or alternative therapies including herbal supplements, taken by the patient and significant non-drug therapies (including physical therapy and blood transfusions) administered from 2 weeks prior to recruitment and during the Follow up assessments.

